LIST OF IN-TEXT FIGURES

Figure 3-1. Study Design 29
Figure 6-1. Suggested Schedule for Key Screening and Baseline Procedures..... 46

PROTOCOL SYNOPSIS

Gilead Sciences, Inc.
[name]
[name]

Study Title: A Phase 2b, Dose-Ranging Study of the Effect of GS-5745 on FEV₁ in Adult Subjects with Cystic Fibrosis

IND Number: 120100
EudraCT Number: 2015-002192-23
Clinical Trials.gov Identifier: NCT02759562

Study Centers Planned: Up to 75 sites globally

Objectives: The primary objective of this study is as follows:

- To evaluate the effect of GS-5745 on pre-bronchodilator forced expiratory volume in 1 second (FEV₁) % predicted in subjects with cystic fibrosis (CF) after 8 weeks of treatment

The secondary objectives of this study are as follows:

- To assess safety, tolerability, and pharmacokinetics (PK) of GS-5745 in subjects with CF
- To evaluate the effect of GS-5745 on post-bronchodilator forced expiratory volume in 1 second (FEV₁) % predicted in subjects with CF after 8 weeks of treatment

Exploratory objectives of this study are as follows:

PPD [REDACTED]

[REDACTED]

[REDACTED]

PPD [REDACTED]

[REDACTED]

[REDACTED]

[REDACTED]

Study Design:

This is a Phase 2b, randomized, double-blind, placebo-controlled, multiple-center, multiple dose study comprising of 2 parts.

[figure not shown]
Part 1 will enroll 60 subjects in a 1:1 ratio to receive weekly subcutaneous (SC) injections of either 600 mg GS-5745 or placebo for 8 weeks.

Upon successful completion of Part 1, Part 2 will enroll 90 subjects in a 1:1:1 ratio to receive weekly SC injections of either 300 mg of GS-5745, 150 mg of GS-5745, or placebo for 8 weeks.

Safety and efficacy analyses will be performed for Part 1 after all subjects have completed the Week 8 visit or discontinued from the study. Data monitoring committee (DMC) meetings will occur at multiple times in Part 1 and before completion of Part 2 (see DMC Section 8.11). Visits and procedures for both Part 1 and Part 2 will be the same.

Subjects enrolled into either Part 1 or Part 2 will have the option of participating in an open-label extension (OLE) at the Week 8 visit. The open-label extension will allow an additional 16 weeks of dosing with GS-5745 600 mg SC weekly in Part 1 and 300 mg SC in Part 2.

Study Design Schema

There will be a FRI sub-study for both Part 1 and Part 2 which will require 2 FRI scans (at Baseline and at the Week 8 visit). A subset of study sites will be trained in FRI. All subjects enrolling into the study at those sites will participate in the FRI sub-study up to 35 subjects in Part 1 and up to 52 subjects in Part 2 to account for an attrition rate of 15%.

There will be a sputum cytology sub-study for both Part 1 and Part 2. A subset of select sites will perform sputum cytology slide preparation from induced sputum samples to investigate changes in total cell count and cell count differential in sputum. No additional procedures will be required of subjects participating in the sputum cytology sub-study.

PPD

Number of
Subjects Planned: Up to 150 subjects

Target
Population: Subjects with CF \geq 18 years of age

Duration of
Treatment: Subjects will receive weekly SC injections for 8 weeks. Subjects completing either Part 1 or Part 2 will be invited to participate in an OLE and will receive an additional 16 weeks of weekly SC injections of GS-5745. All subjects will be followed for 30 days after the last dose of study drug.

Diagnosis and
Main Eligibility
Criteria:

Main Inclusion Criteria

- Male or female 18 years of age or older
- Confirmed diagnosis of CF as determined by the 2008 Cystic Fibrosis Foundation Consensus Report {Farrell et al 2008} criteria
- Subjects must be able to perform acceptable and reproducible spirometry as per the American Thoracic Society (ATS) guidelines
- Must have a body weight of > 40 kg (88.2 lb) at study Screening
- Pre-bronchodilator FEV₁ $\geq 40\%$ and $\leq 80\%$ of predicted at Screening
- Two pre-bronchodilator spirometry measures taken at least 4 days apart (one during Screening, one at Baseline) using the sponsor provided central spirometry equipment must meet the following 2 criteria:
 - The relative difference of FEV_{1(L)}, calculated as the absolute value of [(first FEV₁ – second FEV₁) / first FEV₁] x 100 should be $< 12\%$ **AND**
 - The absolute difference in FEV₁ should be < 200 ml
- Negative Investigation/History of Important Bacteria Infections:
 - Tuberculosis (TB):**
 - A negative QuantiFERON-TB Gold test during Screening
 - Non-Tuberculous Mycobacteria species (NTM):**
 - All sputum cultures for **ANY** *Mycobacterium spp.* performed within 24 months prior to Screening must be negative. If only 1 NTM culture was performed within 24 months prior to Screening, that NTM culture and the most recent NTM culture obtained >24 months prior to Screening both must be negative **AND**

- A negative sputum culture \leq 12 months **prior to** Screening for any *Mycobacterium spp.* **AND**
 - No current treatment for active NTM during Screening
- Burkholderia spp.***
- All sputum/throat cultures for ANY *Burkholderia spp.* performed 24 months prior to Screening must be negative. If only 1 *Burkholderia* culture was performed 24 months prior to Screening, that *Burkholderia spp.* culture and the most recent *Burkholderia spp.* culture obtained >24 months prior to Screening must both be negative **AND**
 - A negative culture for *Burkholderia spp.* during Screening **AND**
 - No current treatment for *Burkholderia spp.* during Screening
- Clinically stable with no evidence of significant respiratory symptoms that would require administration of IV antibiotics, oxygen supplementation, or hospitalization within 30 days of Baseline.
 - A chest radiograph, computed tomography (CT), or magnetic resonance imaging (MRI) within 90 days of Baseline, interpreted as showing no acute findings such as infiltrates [lobar or diffuse interstitial], pleural effusion, or pneumothorax, and no significant intercurrent illness; chronic, stable findings (eg, chronic scarring or atelectasis) are allowed. If not available then a chest radiograph at Screening will be obtained and should be interpreted as above.
 - On stable CF chronic medical regimen for at least 30 days prior to Baseline and expected to remain stable through the completion of the study. This includes but is not limited to: chronic azithromycin use, inhaled bronchodilators, inhaled corticosteroids, inhaled dornase alpha, inhaled hypertonic saline, inhaled mannitol, ivacaftor, and/or ivacaftor/lumacaftor.
 - Inhaled antibiotics (ie, tobramycin, aztreonam, colistin) should be stable for 2 “on-treatment cycles” to be considered a stable CF medication (ie, approximately 2 months if they are taken as continuous inhaled antibiotics or approximately 4 months if they are taken as an alternating inhaled antibiotic).
 - Must have the ability to understand and sign a written informed consent form, which must be obtained prior to initiation of study procedures

Main Exclusion Criteria

- Concurrent use of oral antibiotics (excluding the use of chronic oral azithromycin) or IV antibiotics within 30 days of Baseline. Prophylactic and chronic doxycycline use is prohibited during the study.
- Hospitalization for a respiratory event within 30 days of Baseline
- Current use of systemic immunosuppressive drugs including oral corticosteroids within 30 days of Baseline
- Current requirement for daily continuous oxygen supplementation or requirement (medically necessary) of more than 2 L/minute at night (subject would not meet this exclusion criterion if supplemental oxygen is used for comfort only)
- History of solid organ (including lung) or hematologic transplant, or currently on a transplant waiting list
- Laboratory parameters at screening:
 - Abnormal liver function tests defined as > 3 times the upper limit of normal (ULN) of any of the following: serum aspartate transaminase (AST), serum alanine transaminase (ALT), gamma-glutamyl transpeptidase (GGT), and serum alkaline phosphatase.
 - Total bilirubin > 2 times the ULN
 - Hemoglobin < 10 g/dL for females and < 11.5 g/dL for males at Screening
 - Estimated glomerular filtration rate (eGFR) <40 mL/1.73 m² based on the 4-variable Modification of Diet in Renal Disease (MDRD) formula: $GFR = 175 \times [SCr]^{-1.154} \times [age]^{-0.203} \times [1.212 \text{ if patient is African American}] \times [0.742 \text{ if patient is Female}]$ {Levey et al 2006}

Study Procedures/ Frequency:

The following procedures will be performed during the main study and the optional OLE phase. For subjects who do not elect to roll over onto the OLE, they will complete Week 8 study procedures, followed by the 30-day follow up visit. All post Week 8 study visits and assessments are only applicable to subjects participating in the OLE phase.

Vital Signs (VS): Blood pressure, pulse, respiratory rate, temperature, and weight will be captured at each visit with the exceptions of the PK visits (Day 5) and (Day 48).

Height: Height will be measured at Screening.

Physical exam (PE): Complete PE will be performed at Screening and the 30-day Follow-up visit.

Centralized Spirometry: In the screening period 1 pre-bronchodilator spirometry will be conducted.

At all other visits, Baseline through Follow-up, where spirometry is indicated, spirometry will be collected both pre- and post-bronchodilator. Subjects will withhold their standard of care inhaled CF therapies including bronchodilators prior to study specific spirometry.

Peak Expiratory Flow (PEF) Stability: Peak expiratory flow rate (PEFR) measurements will be collected and recorded each morning (AM) by subjects before their AM bronchodilator during the screening period to calculate their PEF stability limit. Subjects will perform and recorded daily PEF values for at least 7 days to determine the mean AM pre bronchodilator PEF value. This value will be used to determine a > 30% drop in PEF prior to study drug administration.

Oxygen Saturation: Oxygen saturation will be measured at Baseline, Week 8, and at the 30 Day Follow-up Visit.

Spontaneous Sputum Collection: Spontaneous sputum will be collected from all subjects for analysis of microbiology (dominant species and CFU). Collection will occur at Screening and at Weeks 2, 6 in the blinded phase of the study, and Week 20 in the OLE of the study.

Induced Sputum: The induced sputum will be processed for Biomarker analysis including, but not limited to, total and free MMP9, and MMP9 activity. Collection will occur at Baseline, Weeks 4, 8, 12, and 24, and at the 30-Day Follow-up Visit. A sub-set of select sites will perform sputum cytology slide preparation from induced sputum samples.

FRI Sub-study Only: Approximately 30 subjects (15 on 600 mg GS-5745 and 15 on placebo) enrolled into Part 1 of the study will have FRI performed once at Baseline and again at Week 8. Subjects will withhold their standard of care inhaled CF therapies the AM of the FRI and receive standardized doses of inhaled albuterol/salbutamol prior to FRI. If the study proceeds to Part 2, approximately 15 subjects in each treatment arm (300 mg GS-5745, 150 mg GS-5745, and placebo) will have FRI performed once at Baseline and again at Week 8.

Cystic Fibrosis Questionnaire-Revised (CFQ-R): The CFQ-R will be performed prior to any other study related procedures at Baseline, Weeks 2, 4, 6, 8, 12, 16, 20, 24, early termination visit, and at the 30-day Follow-Up visit.

Treatment Satisfaction Questionnaire for Medication (TSQM) (If available): The questionnaire will be performed prior to any other study related procedures at Baseline, and on Weeks 4, 8, 12, 16, 20, 24, and at the early termination visit.

Sino-Nasal Outcome Test (SNOT-22) (If available): The questionnaire will be performed prior to any other study related procedures at Baseline and Weeks 8, 24, and at the early termination visit.

Pulmonary Exacerbation Evaluation: A modified version of the Fuchs criteria {Ramsey et al 2011, Wainwright et al 2015} will be used for categorization of pulmonary exacerbations at Baseline, Weeks 1, 2, 4, 6, 8, 9, 10, 12, 16, 20, 24, and at the early termination visit.

PK Blood Draws: Performed 2 hours after study drug administration at Baseline. Pharmacokinetic blood draws will be performed prior to study drug administration on Weeks 1, 2, 4, 6, 8, and at the early termination visit.

PK Sub-study: PPD

Anti-drug Antibodies (ADA): Baseline, Weeks 4, 8, 16, and 24, and at the 30-day Follow-Up Visit.

Safety Laboratory Tests: Complete blood count (CBC) with differential, chemistry panel will be collected at Screening, Baseline, Weeks 2, 4, 8, and 16, and at the Follow-up visit. Urinalysis will be collected at Screening, Baseline, Weeks 2, 8, and 16, and at the Follow-up visit.

Erythrocyte Sedimentation Rate (ESR): Collected at Screening, Week 8 and Week 24, and will be analyzed at the local lab.

Urine Cotinine: Screening and Weeks 4, 8, and 16.

Serum β -HCG (females of childbearing potential only): Screening and at the 30-Day Follow-Up Visit.

Urine Pregnancy Tests (females of childbearing potential only): Urine pregnancy tests will be performed at Baseline and at Weeks 2, 4, 6, 8, 9, 10, 12, 16, 20, and 24.

12-Lead ECG: Screening, Baseline, Week 4, 8, 16, 24, and the 30-day Follow-up visit.

Blood Biomarker Samples: Blood for biomarkers will be collected at Screening, Baseline, Weeks 2, 4, and 8, and at the 30-day Follow-up visit. Biomarker analysis will include but not limited to total and free MMP9, and MMP9 activity. A blood sample will be collected for RNA to study gene expression at Baseline, Weeks 4 and 8, Early Termination visit and at the 30-day Follow-up visit. Blood will also be collected from all subjects at Baseline for CF genotyping for subjects who do not have a historical genotyping available.

Optional Genomic Testing: PPD

Test Product, Dose, and Mode of Administration:	
GS-5745 drug product is a sterile, clear, aqueous buffered solution. GS-5745 will be supplied as 150 mg/mL solution in a single-use, pre-filled syringe intended to deliver a 1.0 mL SC injection.
 
Subjects in Part 1 randomized to GS-5745 will receive 600 mg (4 SC injections of GS-5745) per dose. Subjects randomized to GS-5745 in Part 2 will receive either 300 mg (2 SC injections of GS-5745) or 150 mg (1 SC injection of GS-5745 and 1 SC injection of placebo).

Reference Therapy, Dose, and Mode of Administration:	
Matched placebo administered by SC injection.
 
Subjects randomized to placebo in Part 1 will receive 4 SC injections per dose. Subjects randomized to placebo in Part 2 will receive 2 SC injections per dose.

Criteria for Evaluation:	
Safety:	Safety evaluation will be assessed by adverse events (AEs), concomitant medications, clinical laboratory tests, vital signs, ECG data, and ADA data.
Efficacy:	The primary endpoint is absolute change in pre-bronchodilator FEV ₁ percent predicted from Baseline to Week 8 of the study.
Pharmacokinetics:	Plasma concentrations of GS-5745 will be determined.
Statistical Methods:	
Primary Endpoint:
 
The primary endpoint, the absolute change in pre-bronchodilator FEV₁ percent predicted from Baseline to Week 8, will be analyzed using a mixed effect model for repeated measure (MMRM) for Part 1 and Part 2 respectively. The model for each part of the study will include treatment, Baseline FEV₁ percent predicted level, visit and treatment-by-visit interaction as fixed effect, and subject as a random effect. Estimated least square means of treatment effects and estimated differences in treatment effects between GS-5745 treatment group and placebo group at Week 8 will be presented with the 90% confidence intervals (CIs) and adjusted p-values.
 
Safety evaluation will be assessed by AEs, concomitant medications, clinical laboratory tests, vital signs, ECGs and ADA data.

GS-5745 concentrations and PK parameters (as applicable) will be listed and summarized using descriptive statistics.

Sample Size Justification:

A sample size of 25 evaluable subjects per arm for Part 1 and Part 2 will provide 80% power to detect a difference of 5% change from Baseline in percent predicted FEV₁ between GS-5745 active treatment and placebo with a 2-sided alpha level of 0.1 assuming a common standard deviation (SD) of 7% {[Brouwer et al 2014](#), [Ramsey et al 2011](#), [Retsch-Bogart et al 2009](#)}. To compensate for early drop out, 30 subjects per arm will be enrolled assuming an attrition rate of 15%.

With respect to the sub-study in FRI, a sample size of 15 subjects on GS-5745 and 15 subjects on placebo provides more than 90% power to detect a 6% difference in FRI measurements (approximating an absolute change of 3% in FEV1) between the GS-5745 and the placebo arms in FRI change from Baseline based on a 2-sample t-test at a 2-sided alpha level of 0.1. The calculation assumes the SD of FRI change being 5% for the GS-5745 arm and 2% for placebo arm, as the FRI response is expected to be more heterogeneous in the treatment group. To compensate for early drop out, up to 35 subjects in Part 1 and up to 52 subjects in Part 2 will be enrolled assuming an attrition rate of 15%.

DMC Meetings

A total of 4 scheduled DMC meetings will occur throughout Part 1 and prior to the end of Part 2 of the study.

- Part 1: Safety Analysis #1 after 10 subjects have completed Week 2 Visit or early discontinued from the study
- Part 1: Safety Analysis #2 after 30 subjects have completed Week 8 Visit or early discontinued from the study
- Part 1: Safety Analysis #3 and Interim Efficacy Analysis after all randomized subjects have completed Week 8 Visit or early discontinued from the study
- Part 2: Safety Analysis #4 after 45 subjects have completed Week 8 Visit or early discontinued from the study

The detail is outlined in Section 8.11 with the corresponding GO/NO GO decision criteria.

This study will be conducted in accordance with the guidelines of Good Clinical Practice (GCP) including archiving of essential documents.

GLOSSARY OF ABBREVIATIONS AND DEFINITION OF TERMS

ABPA	allergic bronchopulmonary aspergillosis
ADA	anti-drug antibodies
AE	adverse event
ALT	alanine transaminase
AST	aspartate transaminase
ATS	American Thoracic Society
BAL	bronchoalveolar lavage
CBC	complete blood count
CF	cystic fibrosis
CFU	colony forming units
CFQ-R	Cystic Fibrosis Questionnaire – Revised
CFR	Code of Federal Regulations
CFTR	CF transmembrane conductance regulator
CI	confidence interval
COPD	chronic obstructive pulmonary disease
CRF	case report form
CRO	contract research organization
CSR	clinical study report
CT	computed tomography
CTCAE	Common Terminology Criteria for Adverse Events
DSPH	Drug Safety and Public Health
DMC	data monitoring committee
EC	ethics committee
eCRF	electronic case report form
ECG	Electrocardiogram
ELISA	enzyme-linked immunosorbent assay
ESR	Erythrocyte Sedimentation Rate
FDA	US Food and Drug Administration
FEF ₂₅₋₇₅	forced expiratory flow at 25-75%
FEV ₁	forced expiratory volume in 1 second
FRC	functional residual capacity
FRI	functional respiratory imaging
FSH	follicle stimulating hormone
FVC	forced vital capacity
GCP	good clinical practice
GGT	gamma-glutamyl transpeptidase
GMP	good manufacturing process
hCG	human chorionic gonadotropin

HIV	human immunodeficiency virus
HLGT	high-level group term
HLT	high-level term
HSP	Hysterosalpingogram
IB	Investigator Brochure
ICH	International Conference on Harmonisation
IEC	independent ethics committee
IMP	investigational medicinal product
IRB	institutional review board
IUD	intrauterine device
IV	Intravenous
IWRS	interactive web response system
IXRS	interactive web/voice response system
kDa	kiloDalton
LABA	long acting beta agonist
LLT	lower-level term
MedDRA	Medical Dictionary for Regulatory Activities
MMP9	matrix metalloproteinase 9
MMRM	mixed effect model for repeated measure
MRI	magnetic resonance imaging
mSv	Millisievert
NPD	nasal transepithelial potential difference
NTM	nontuberculosis mycobacterium
PA	Pseudomonas aeruginosa
PE	physical exam
PEF	peak expiratory flow
PEFR	peak expiratory flow rate
PFS	pre-filled syringe
PGP	Proline-Glycine-Proline
PK	Pharmacokinetics
PT	Preferred term
RSS	Respiratory Symptom Scale
SAP	Statistical analysis plan
SABA	short-acting beta agonist
SADR	serious adverse drug reaction
SAE	serious adverse event
SAMA	short-acting muscarinic antagonist
SC	Subcutaneous
SD	standard deviation
SNOT-22	Sino-Nasal Outcome Test

SOC	system organ class
SOP	standard operating procedure
SUSAR	suspected unexpected serious adverse reaction
TLC	total lung capacity
TSQM	Treatment Satisfaction Questionnaire for Medication
UC	ulcerative colitis
ULN	upper limit of normal
US	United States
VS	vital signs

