3.3. Study Treatments

3.3.1. Part 1

Subjects who meet the eligibility criteria at screening will be randomized in a blinded fashion in a 1:1 ratio as follows:

- Treatment arm (n=30): 600 mg GS-5745 (4 SC injections of 150 mg as 1 dose given weekly for 8 doses).
- Placebo arm (n=30): matching placebo (4 SC injections as 1 dose given weekly for 8 doses).

3.3.2. Part 2

Subjects who meet eligibility criteria at screening will be randomized in a blinded fashion in a 1:1:1 ratio as follows:

- Treatment arm 300 mg (n=30): 300 mg GS-5745 (2 SC injections of 150 mg as 1 dose given weekly for 8 doses).
- Treatment arm 150mg (n=30): 150 mg GS-5745 (1 SC injection of 150 mg and 1 SC injection of placebo as 1 dose given weekly for 8 doses).
- Placebo arm (n=30): matching placebo (2 SC injections as 1 dose given weekly for 8 doses).

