3.4. Duration of Treatment

Randomized subjects in both Part 1 and Part 2 will complete 8 weeks of weekly dosing. Subjects that choose to participate in the OLE will receive an additional 16 weeks of weekly dosing of GS-5745 for a total of 24 weeks of dosing. Subjects will have their final visit 30 days after the last dose of study drug.

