3.5. Protocol Discontinuation Criteria

Study drug administration will be suspended in all subjects if any one of the following criteria are met:

- 1) The Principal Investigator (or his/her deputy) and the Sponsor consider the number and/or severity of AEs justify discontinuation of the study
- 2) The Sponsor makes a unilateral request to do so
- 3) An SAE or a confirmed Grade 4 laboratory finding in the same system organ class and determined to be related to study drug occurs in 2 or more subjects in a cohort.
- 4) Laboratory results that meet Hy's Law criteria {[U.S. Department of Health & Human Services \(DHHS\) et al 2009](#)}

Decisions to reinstate dosing will be made by the DMC and Sponsor upon review of all available safety and tolerability data generated by subjects dosed to date.

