6.1. Details of Study Visits

6.1.1. Subject Enrollment and Treatment Assignment

It is the responsibility of the Investigator to ensure that subjects are eligible to participate in the study prior to randomization or enrollment and throughout the study.

Once consent has been obtained, all screening tests and procedures have been assessed, and study eligibility has been confirmed, eligible subjects will be randomized to study treatment as described in [Section 3.3](#).

The study center will not be released to initiate dosing until:

- The Institutional Review Board (IRB) or Ethics Committee (EC) reviewed and approved the study and the informed consent document;
- All required regulatory documents have been submitted to and approved by Gilead or the CRO;
- A master services agreement and/or study agreement is executed;
- The site initiation meeting has been conducted by the Gilead clinical monitor (or designee). The initiation meeting will include a review of the protocol, the IB, and investigator responsibilities.

Table 6-1. Schedule of Assessments

[figure not shown]
Week	Screening	Baseline Randomization	Optional PK	Study Drug Administration Visits						Optional PK	Study Drug Administration Visit	Primary Endpoint	Optional Open-Label Extension						30-Day Follow-Up Visit	Early Termination Visit	
				1	2	3	4	5	6				7	8	9	10	11, 13-15, 17-19, 21-23	12			16
Day	-30 to -1	1 ¹	5	8	15	22	29	36	43	48	50	57	64	71		85	113	141	169		
Window in days			±1	±3	±3	±3	±3	±3	±3	±1	±3	-3 to +4	±3	±3	±3	±3	±3	±3	±3	±7	
Home Health Visit Option						X		X		X	X				X						
Withhold all inhaled CF therapies morning of study visit	X ⁹	X		X			X		X			X		X			X		X	X	
Written Informed Consent	X																				
CFQ-R ^a		X			X		X		X			X				X	X	X	X	X	X
TSQM (if available) ^a		X					X					X				X	X	X	X		
SNOT-22 (if available) ^a		X										X							X		
Medical History	X																				
Concomitant Medications	X	X	X	X	X	X	X	X	X	X		X	X	X		X	X	X	X	X	X
Pulmonary Exacerbation Evaluation		X		X	X		X		X			X	X	X		X	X	X	X	X	
Complete Physical Exam ^b	X																			X	X
Symptom Driven Physical Exam ^b		X					X					X				X	X	X	X		
Vital Signs	X	X		X	X	X	X	X	X		X	X	X	X		X	X	X	X	X	X
Blood for Safety Labs ^c	X	X			X		X					X					X			X	X
ESR ^f	X											X								X	
Urine Cotinine	X						X					X					X				
Urinalysis	X	X			X							X					X			X	X
Serum Pregnancy Test ^d	X																			X	X
Urine Pregnancy Test		X			X		X		X			X	X	X		X	X	X	X		
Oxygen Saturation		X										X								X	X

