Screening Spirometry	X ^m																				

Week	Screening	Baseline Randomization	Optional PK	Study Drug Administration Visits						Optional PK	Study Drug Administration Visit	Primary Endpoint	Optional Open-Label Extension						30-Day Follow-Up Visit	Early Termination Visit	
				1	2	3	4	5	6				7	8	9	10	11, 13-15, 17-19, 21-23	12			16
Day	-30 to -1	1 ¹	5	8	15	22	29	36	43	48	50	57	64	71	85	113	141	169			
Window in days			±1	±3	±3	±3	±3	±3	±3	±1	±3	-3 to +4	±3	±3	±3	±3	±3	±3	±3	±7	
Home Health Visit Option						X		X		X	X				X						
Pre- and post-bronchodilator Spirometry ^e		X			X		X		X			X		X			X		X	X	X
PEFR	X	X ^p		X		X		X			X				X		X				
Chest X-ray ^f	X																				
ECG	X	X					X				X					X		X	X		
Induced sputum for biomarkers		X					X				X				X			X	X	X	
Spontaneous sputum for microbiology ^g	X, X				X				X								X				
FRI Scan ^h		X									X										
Blood for PK ⁱ		X		X	X		X		X		X									X	
PK sub-study			X						X												
Anti-drug Antibodies		X					X				X					X		X	X	X	
Blood for Biomarkers	X	X			X		X				X								X	X	
Blood for RNA Biomarkers		X					X				X								X	X	
Blood for CF genotyping ^l		X																			
Optional blood sample for genomic research ^l		X																			
Randomization		X																			
Study drug administration ^k		X		X	X	X	X	X	X		X	X ⁿ	X-weekly through week 23-X								
Adverse Events	X	X	X	X	X	X	X	X	X	X	X	X	X ^o	X ^o	X ^o	X ^o	X ^o	X	X	X	
Musculoskeletal Symptom Assessment	X	X					X				X				X	X	X	X	X		

a Questionnaires should be obtained prior to any other procedures. At visits where there are multiple questionnaires, the CFQR should be completed first, then SNOT-22 and then TSQM. If on a given visit SNOT-22 is not done then the CFQ-R is completed first and then the TSQM.

- b Includes height at screening visit and weight at all visits and to be conducted prior to dosing. A complete physical examination will be performed at screening and the 30-day Follow-up Visit. A symptom-driven physical examination will be performed at the Baseline, Week 4, 8, 12, 16, 20 and 24, and can be performed as needed at other study visits.
- c Safety labs include CBC with differential, chemistry panel.
- d For female subject post-menopausal for less than 2 years, if FSH < 40 mIU/ mL a serum pregnancy test will be required.
- e Subjects will withhold their standard of care inhaled CF therapies prior to study specific spirometry

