#### 7.2.2.2. Summaries of Laboratory Abnormalities

The summaries (number and percentage of subjects) for treatment-emergent laboratory abnormalities will be provided by lab test, treatment group and study phase; subjects will be categorized according to the most severe postbaseline abnormality grade for a given lab test.

For all summaries of laboratory abnormalities, the denominator is the number of subjects with nonmissing postbaseline values within study period.

A by-subject listing of treatment-emergent laboratory abnormalities will be provided by subject ID number and visit in chronological order. This listing will include all test results that were collected throughout the study for the lab test of interest, with all applicable severity grades displayed.

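### Subjects who complete the open-label extension have no scheduled safety laboratory panel between Week 16 and the 30-day follow-up (79 days nominally, 7 or 8 of 24 doses), and the follow-up panel may fall outside the SAP's counting window

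*Protocol*

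**What the plan says.** The synopsis gives the blood schedule as "chemistry panel will be collected at Screening, Baseline, Weeks 2, 4, 8, and 16, and at the Follow-up visit" and the urine schedule as "Urinalysis will be collected at Screening, Baseline, Weeks 2, 8, and 16, and at the Follow-up visit". The row "Blood for Safety Labs" in protocol Table 6-1, read by column, agrees. It is marked at Screening, Baseline, Weeks 2, 4, 8 and 16, the 30-day follow-up and Early Termination, and is blank at Weeks 20 and 24. The footnote to that row reads "Safety labs include CBC with differential, chemistry panel". SAP Appendix 1 reproduces the same pattern.

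On dosing, Section 3.3 gives the blinded regimen as "4 SC injections of 150 mg as 1 dose given weekly for 8 doses" (the 600 mg arm). Section 3.4 says that subjects who enter the OLE "will receive an additional 16 weeks of weekly dosing of GS-5745 for a total of 24 weeks of dosing". Table 6-1 shows weekly administration through Week 23. Section 6.1.8 puts the follow-up visit 30 days after the last dose, with a ±7-day window in Table 6-1.

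Two parts of the plan use these results. Protocol Section 3.5 lists "Laboratory results that meet Hy's Law criteria" among the grounds for suspending dosing in all subjects, together with certain related, confirmed Grade 4 laboratory findings. SAP 7.2.2.2 says that summaries of "treatment-emergent laboratory abnormalities will be provided by lab test, treatment group and study phase", and SAP 7.2.2.1 limits the values counted to those up to the last dose plus 30 days.

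**The concern.** The OLE lasts 16 weeks and has one scheduled safety panel between its first and last dose. Subjects randomized to placebo first receive active drug at Week 8, so Week 16 is their only scheduled panel during active dosing, and about half of their active doses come at or after it.

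No panel is scheduled at Week 24, the first visit after the last dose, although blood is drawn there for anti-drug antibodies. An abnormality that arose late and resolved by follow-up would not be recorded by scheduled sampling. One first seen at follow-up might not be counted, depending only on the day of the visit. A subject withdrawn from the study after Week 16, by contrast, is to have a panel at Early Termination if possible (Section 6.1.9). The open-label laboratory table would therefore rest on different sampling for the two groups.

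**Working it through.** **Inputs.** Laboratory visits: synopsis, Table 6-1 and SAP Appendix 1. Doses: Sections 3.3 and 3.4 and Table 6-1. Follow-up timing: Section 6.1.8 and Table 6-1. Counting window: SAP 7.2.2.1. Nominal study day = 1 + 7 × week.

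**Dose count, reproducing the plan's figure.** Baseline and Weeks 1 to 7 give 8 doses. Weeks 8 to 23 give 23 − 8 + 1 = 16. The total is 8 + 16 = 24, as Section 3.4 states.

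**Nominal days.**
- Week 16: 1 + 7 × 16 = Day 113
- Last dose, Week 23: 1 + 7 × 23 = Day 162
- Week 24: 1 + 7 × 24 = Day 169
- Follow-up: 162 + 30 = Day 192; with ±7 days, Days 185 to 199

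**Intervals between scheduled panels.**

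| Period | Days | Longest interval |
|---|---|---|
| Blinded, blood (Week 4 to Week 8) | 29 to 57 | 28 days |
| Blinded, urine (Week 2 to Week 8) | 15 to 57 | 42 days |
| OLE, both (Week 8 to Week 16) | 57 to 113 | 56 days |
| OLE completers, both (Week 16 to follow-up) | 113 to 192 | 79 days |

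The 79 days are 162 − 113 = 49 days to the last dose plus 30 days after it. With the follow-up window and Week 16 on its nominal day, the range is 185 − 113 = 72 to 199 − 113 = 86 days.

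**Doses in the interval.** If the Week 16 sample is drawn before that day's dose, Weeks 16 to 23 give 8 of 24. If it is drawn after, Weeks 17 to 23 give 7 of 24. The documents fix pre-dose timing for PK samples (Table 6-1 footnote) and for safety blood at Baseline (Section 6.1.3), but not for safety blood at Week 16.

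**Counting window.** The SAP window closes at Day 162 + 30 = Day 192. The visit window runs to Day 199, so a visit on Days 193 to 199 (31 to 37 days after the last dose) is on schedule but its panel is not countable. SAP 3.8.1 places data from the date of the first open-label dose in the open-label period, so a Week 8 panel drawn on that date is included. It is nevertheless taken before that dose and adds nothing after Week 16.

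**With a panel at Week 24.** The intervals become 169 − 113 = 56 days and 192 − 169 = 23 days, so the longest falls from 79 to 56. Day 169 is 7 days after the last dose (4 to 10 days with the ±3-day Week 24 window and a Day 162 last dose), well inside the counting window.

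**The case against.** The strongest reply is that this is a deliberate choice of lighter monitoring in an uncontrolled extension. The protocol reports no drug-related safety signal to date (Section 1.2.3) and no findings of toxicological concern in 26-week animal studies (Section 1.2.2). Late in the OLE it still schedules adverse events, vital signs, symptom-driven examination and musculoskeletal assessment at Weeks 20 and 24, and ECG and anti-drug antibodies at Week 24. The synopsis and Section 6.3.12.4 also place ESR at Week 24. Unscheduled laboratory tests are not excluded. All of this stands, and it limits the point to CBC, chemistry and urinalysis. It does not give a reason for omitting the panel at a visit where blood is already drawn.

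A reader might infer that the laboratory schedule contradicts Section 3.4 or 3.5. It does not. Section 3.4 states a duration and Section 3.5 states triggers; neither sets a laboratory frequency, and the three versions of the schedule agree. A reader might also infer that a Week 24 panel would let the Section 3.5 laboratory triggers operate late in the OLE. For a given subject it would not, because it follows that subject's last dose.

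The contrast with early terminators should not be pressed far. The Early Termination panel applies to withdrawal from the study, not to stopping drug alone, and only if possible. The documents do not say whether it is additional to the follow-up visit. With no randomized control in the OLE, no treatment comparison is biased. Nor do the documents show that drug has cleared by 30 days, so the follow-up sample cannot be called a washout sample.

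Finally, the SAP plans no inferential analysis and no descriptive laboratory statistics, and it lists hematology and chemistry results by subject. A late follow-up value in those tests would still be visible in a listing. That reduces the consequence in this study without closing the gap.

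**Conclusion.** The point holds as a coverage gap in scheduled data collection for OLE completers. Its size is a nominal 79 days without a safety panel, spanning 7 or 8 of 24 doses, against earlier maxima of 28 days (blood) and 42 days (urine) in the blinded phase and 56 days in the OLE. A completer seen 31 to 37 days after the last dose has no panel after Week 16 that the SAP can count. The loss at that edge comes from the SAP definition; protocol Section 8.6.3 counts abnormalities at any time after Baseline.

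The figures assume nominal visit days, all 16 open-label doses given, and a last dose at Week 23. The blinded phase and the 8-week primary endpoint are untouched. The SAP reports termination after 6 enrolled subjects, so the practical effect is confined to any who continued in the OLE past Week 16.

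**What to change.** As a data-collection change, mark the existing safety panel and urinalysis in the Week 24 column of Table 6-1, in the synopsis and in SAP Appendix 1. Completers then have an end-of-treatment value inside the treatment-emergent window, and the open-label laboratory table includes it. The cost is one laboratory kit and a urine sample per OLE completer, with no new visit or venepuncture.

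This adds no result during Weeks 17 to 23. The sponsor should consider separately whether the laboratory schedule supports the laboratory-based suspension criteria in Section 3.5; no clinical rule is proposed here.

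For the present study, state beside the open-label laboratory table that completers had no scheduled panel between Week 16 and follow-up and that follow-up values more than 30 days after the last dose are not counted. Correct the schedule before the protocol is reused.
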